5.1.1 Subject Inclusion Criteria

Patients must have histologically confirmed SMM based on the following criteria:

(A) Mayo clinic criteria (patient must have at least 2 risk factors present)¹⁴:

1. Bone marrow core biopsy plasma cell involvement by CD138 immunohistochemistry $\geq 10\%$
2. Monoclonal spike ≥ 3 g/dL
3. Free light chain ratio in serum < 0.125 or > 8 .

*2 of 3 risk factors: intermediate risk for progression at a rate of 51% at 5 years

*3 of 3 risk factors: high risk for progression at a rate of 76% at 5 years

OR

(B) PETHEMA criteria (patient must have at least 1 risk factor present)¹³

1. $\geq 95\%$ abnormal plasma cells/total plasma cells in bone marrow compartment
2. Immunoparesis

*1 of 2 risk factors: intermediate risk for progression at a rate of 46% at 5 years

*2 of 2 risk factors: high risk for progression at a rate of 72% at 5 years

OR

(C) SWOG criteria (patient must have 2 risk factors present or one risk factor if this risk factor if a GEP70 score of > 37.2)¹⁵

1. Monoclonal spike ≥ 3 g/dL
2. Involved free light chain ≥ 25 mg/dL
3. GEP70 risk score > 37.2

* ≥ 2 risk factors: high risk of progression at a rate of 70% at 2 years

* We would also include patients with 1 risk factor as long as this risk factor is GEP70 risk score > 37.2 since patients with this risk factor have an intermediate risk of progression at a rate of 50% at 2 years.

- 5.1.1.1 Creatinine clearance ≥ 50 ml/min. CrCl will be calculated by Cockcroft-Gault method. CrCl (calculated) = $(140 - \text{Age}) \times \text{Mass (in kilograms)} \times [0.85 \text{ if Female}] / 72 \times \text{Serum Creatinine (in mg/dL)}$. If calculated CrCl based on Cockcroft-Gault method is < 50 mL/min, patient will have a 24 hr urine collection to measure CrCl. The measured CrCl must also be ≥ 50 ml/min
- 5.1.1.2 Age ≥ 18 years.
- 5.1.1.3 Eastern Cooperative Oncology Group (ECOG) performance status 0-1
- 5.1.1.4 Absolute neutrophil count (ANC) $\geq 1.0 \times 10^9$ /L, hemoglobin ≥ 10 g/dL and platelet count $\geq 50 \times 10^9$ /L
- 5.1.1.5 Adequate hepatic function with bilirubin < 1.5 x the ULN, and AST and ALT < 3.0 x ULN.
- 5.1.1.6 Subjects must be able to give informed consent
- 5.1.1.7 Female subject of childbearing potential should have a negative urine or serum pregnancy within 72 hours prior to receiving the first dose of study medication. If the urine test is positive or cannot be confirmed as negative, a serum pregnancy test will be required.

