5.1.2 Subject Exclusion Criteria

The subject must be excluded from participating in the trial if the subject has any of the following:

- 5.1.2.1 Evidence of myeloma defining events or biomarkers of malignancy due to underlying plasma cell proliferative disorder meeting at least one of the following¹⁶
 - 1) Hypercalcemia: serum calcium >0.25 mmol/L (>1 mg/dL) higher than the upper limit of normal or > 2.75 mmol/L (> 11 mg/dL)
 - 2) Renal Insufficiency: creatinine clearance < 40 ml/min or serum creatinine > 2 mg/dL
 - 3) Anemia: hemoglobin value <10 g/dL or 2 g/dL < normal reference
 - 4) Bone lesions: one or more osteolytic lesions on skeletal radiography, computerized tomography (CT) or 2-deoxy-2[F-18] fluoro-D-glucose positron emission tomography CT (PET-CT).
 - 5) Clonal bone marrow plasma cell percentage $\geq 60\%$
 - 6) Involved: uninvolved serum free light chain ratio ≥ 100 measured by Freelite assay (The Binding Site Group, Birmingham, UK)
 - 7) >1 focal lesions on MRI studies (each focal lesion must be 5 mm or more in size), if clinically indicated

- 5.1.2.2 Prior or concurrent systemic treatment for SMM.
 - a) Bisphosphonates are permitted.
 - b) Treatment with corticosteroids is not permitted
 - c) Radiotherapy is not permitted.
 - d) Prior treatment for smoldering multiple myeloma with chemotherapy agents approved for the treatment of multiple myeloma is not permitted.
- 5.1.2.3 Plasma cell leukemia
- 5.1.2.4 Pregnant or lactating females. Because there is a potential risk for adverse events in nursing infants secondary to treatment of the mother with pembrolizumab, breastfeeding should be discontinued if the mother is treated with pembrolizumab. These potential risks may also apply to other agents used in this study.
- 5.1.2.5 Has a diagnosis of immunodeficiency or is receiving systemic steroid therapy or any other form of immunosuppressive therapy within 7 days prior to the first dose of trial treatment.
- 5.1.2.6 Has a known history of active TB (Bacillus Tuberculosis)
- 5.1.2.7 Hypersensitivity to pembrolizumab or any of its excipients.
- 5.1.2.8 Has had a prior anti-cancer monoclonal antibody (mAb) within 4 weeks prior to study Day 1 or who has not recovered (i.e., \leq Grade 1 or at baseline) from adverse events due to agents administered more than 4 weeks earlier.

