Pneumonitis	2	Toxicity resolves to Grade 0-1	Toxicity does not resolve within 12 weeks of last dose or inability to reduce corticosteroid to 10 mg or less of prednisone or equivalent per day within 12 weeks.
	3-4	Permanently discontinue	Permanently discontinue
Renal Failure or Nephritis	2	Toxicity resolves to Grade 0-1	Toxicity does not resolve within 12 weeks of last dose or inability to reduce corticosteroid to 10 mg or less of prednisone or equivalent per day within 12 weeks.
	3-4	Permanently discontinue	Permanently discontinue
All Other Drug-Related Toxicity ²	3 or Severe	Toxicity resolves to Grade 0-1	Toxicity does not resolve within 12 weeks of last dose or inability to reduce corticosteroid to 10 mg or less of prednisone or equivalent per day within 12 weeks.
	4	Permanently discontinue	Permanently discontinue
Note: Permanently discontinue for any severe or Grade 3 drug-related AE that recurs or any life-threatening event.			
¹ For patients with liver metastasis who begin treatment with Grade 2 AST or ALT, if AST or ALT increases by greater than or equal to 50% relative to baseline and lasts for at least 1 week then patients should be discontinued.			
² Patients with intolerable or persistent Grade 2 drug-related AE may hold study medication at physician discretion. Permanently discontinue study drug for persistent Grade 2 adverse reactions for which treatment with study drug has been held, that do not recover to Grade 0-1 within 12 weeks of the last dose.			

Dosing interruptions are permitted in the case of medical / surgical events or logistical reasons not related to study therapy (e.g., elective surgery, unrelated medical events, patient vacation, and/or holidays). Subjects should be placed back on study therapy within 3 weeks of the scheduled interruption, unless otherwise discussed with the Sponsor. The reason for interruption should be documented in the patient's study record.

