5.11 Subject Withdrawal/Discontinuation Criteria

Subjects may withdraw consent at any time for any reason or be dropped from the trial at the discretion of the investigator should any untoward effect occur. In addition, a subject may be withdrawn by the investigator or the Sponsor if enrollment into the trial is inappropriate, the trial plan is violated, or for administrative and/or other safety reasons. Specific details regarding discontinuation or withdrawal are provided in Section 8.1.2 – Other Procedures.

A subject must be discontinued from the trial for any of the following reasons:

- The subject or legal representative (such as a parent or legal guardian) withdraws consent.
- Confirmed disease progression
 - Increase in $\geq 25\%$ from best response and/or lowest measurable value in
 - Serum M-component and/or (the absolute increase must be ≥ 0.5 g/dL)
 - Urine M-component and/or (the absolute increase must be ≥ 200 mg/24h)
 - Only in patients without measurable serum and urine M-protein levels: the difference between involved and uninvolved free light chains levels. The absolute increase must be > 10 mg/dl.
 - Bone marrow plasma cell percentage: the absolute % increase must be $\geq 10\%$
 - Definite development of new bone lesions or soft tissue plasmacytomas
 - Development of hypercalcemia (corrected serum calcium > 1 mg/dL higher than the upper limit of normal or > 11 mg/dL) that can be attributed solely to the plasma cell proliferative disorder
 - Rise in serum creatinine by 2 mg/dl or more and/or creatinine clearance > 40 ml/min, that can be attributed solely to the plasma cell proliferative disorder
 - Development of anemia with a hemoglobin 2 g/dl below the lower limit of normal

- Unacceptable adverse experiences as described in Section 5.7.1.2
- Intercurrent illness that prevents further administration of treatment
- Investigator's decision to withdraw the subject
- The subject has a confirmed positive serum pregnancy test
- Noncompliance with trial treatment or procedure requirements
- The subject is lost to follow-up
- Administrative reasons

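### In 5.11 the anemia limb of progression has no attribution condition, so anemia not caused by myeloma would, read literally, require removal as progression; the renal limb beside it has an inverted sign

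*Combined protocol and SAP*

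**What the plan says.** Section 5.11 opens its list of mandatory reasons with "A subject must be discontinued from the trial for any of the following reasons". One reason is confirmed disease progression, with sub-items that include three organ limbs.

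- Hypercalcemia, qualified as due solely to the plasma cell disorder.
- Renal function: a serum creatinine rise of at least 2 mg/dl and/or "creatinine clearance > 40 ml/min, that can be attributed solely to the plasma cell proliferative disorder".
- Anemia, with no qualification: "Development of anemia with a hemoglobin 2 g/dl below the lower limit of normal".

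At entry, exclusion 5.1.2.1 covers the same three organ systems under one lead-in: "Evidence of myeloma defining events or biomarkers of malignancy due to underlying plasma cell proliferative disorder". Its anemia and renal items read "Anemia: hemoglobin value <10 g/dL or 2 g/dL < normal reference" and "Renal Insufficiency: creatinine clearance < 40 ml/min or serum creatinine > 2 mg/dL".

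Drug toxicity has its own rules in 5.7.1.2. For the row "All Other Drug-Related Toxicity", Table 3 holds treatment at Grade 3 or severe, allows restart at Grade 0-1, and discontinues at Grade 4 or if recovery takes more than 12 weeks. Its second footnote leaves a hold for intolerable or persistent Grade 2 events to the physician.

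**The concern.** Two of the three organ limbs ask whether myeloma is the cause; the anemia limb asks only for a hemoglobin value. Hemoglobin can fall for reasons unrelated to myeloma, and the plan recognizes this at entry. On study, the same kind of finding is labelled progression whatever its cause.

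A patient who is still benefiting could therefore lose treatment and be recorded as progressed. The label is hard to undo: the restart option in 2.1 is for responders who chose to stop after 8 cycles, not for patients taken off as progressed. A Table 3 hold, by contrast, allows treatment to resume.

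The renal limb has a separate fault. As printed, its clearance value is met by good renal function and missed by poor renal function.

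**Working it through.** The plan states no figure on this point, so the check is a comparison of texts with a little arithmetic.

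**1. Attribution, limb by limb.**

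| Limb | Trigger in 5.11 | Tied to the plasma cell disorder in 5.11? | Tied at entry (5.1.2.1)? |
|---|---|---|---|
| Calcium | > 1 mg/dL above the upper limit, or > 11 mg/dL | Yes | Yes |
| Renal | Creatinine rise of 2 mg/dl or more, and/or clearance > 40 ml/min | Yes | Yes |
| Anemia | Hemoglobin 2 g/dl below the lower limit | No | Yes |

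So 2 of 3 organ limbs carry the condition in 5.11, against 3 of 3 at entry. No lead-in in 5.11 extends the condition to the whole list. The anemia sentence is complete as it stands and shows no sign of lost words.

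**2. Conflict with the toxicity rule.** Take a drug-related hemoglobin fall that passes the 5.11 trigger, is below Grade 4 and is not a recurrent Grade 3 event. Table 3 gives a hold with restart at Grade 3, or a discretionary hold at Grade 2. The literal 5.11 limb gives removal. The two instructions differ, and neither section says which prevails.

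**3. How near the trigger can be at entry (assumed limits of normal).** The plan gives no lower limit of normal. Inclusion criterion 5.1.1.4 accepts hemoglobin of 10 g/dL or more. The trigger is the lower limit minus 2:

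- limit 12: 12 - 2 = 10 g/dL
- limit 13: 13 - 2 = 11 g/dL
- limit 14: 14 - 2 = 12 g/dL

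With a limit above 12, a patient whose low hemoglobin is not due to myeloma can enter already past the trigger (10 to 11 g/dL for a limit of 13; 10 to 12 g/dL for 14). The limb speaks of anemia developing, which may spare anemia present at entry. The step shows only that the trigger need not be remote.

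**4. Sign of the renal limb.** Entry requires a clearance of at least 50 ml/min; if the calculated value is lower, "The measured CrCl must also be ≥ 50 ml/min". Since 50 > 40, all 16 planned patients, if eligible, exceed the printed value at entry. A patient whose clearance falls to 35 would not meet it. The exclusion criterion has the direction the limb needs: < 40 ml/min.

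**The case against.** The strongest reply is that the list should be read in context. The hemoglobin item sits under a heading that requires confirmed progression, and the next reason in 5.11 is unacceptable adverse experiences under 5.7.1.2. An investigator who knows that a fall is drug-related, or due to bleeding, would use that route. This probably describes good practice, and it is one reason to expect few affected patients. It does not repair the text. 5.11 does not define confirmation, a repeat hemoglobin confirms the value and not the cause, and the toxicity item does not exempt such a fall from the progression item.

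The reply on duration of response is stronger, and most of it stands. A reader might infer that a wrongly removed responder would have the response ended on the wrong date. But 6.2.3 directly follows 6.2.2, whose item (g) is the natural definition of progressive disease. That item has an attribution clause, and the conditions before it cannot be read in the available text. It cannot be said that anemia is missing there or that it is unqualified. Neither list cites the other, so an effect is possible, but it is not shown.

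A reader might also infer that the renal limb as printed would remove every patient. It would not, because that limb carries the attribution condition and a normal clearance cannot be put down to myeloma.

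**Conclusion.** The point holds as an error of wording in 5.11. The anemia limb lacks a condition that the plan applies to the two limbs above it and to anemia at entry, and the clearance sign is inverted. The main consequence is wrongful removal from treatment with a wrong progression label.

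The size cannot be computed. The documents give no rate of anemia from causes other than myeloma, and the number affected is probably small among 16 patients.

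A reader might extend the point to the main results; the documents do not support that. Time to progression and progression-free survival are defined in 6.2.4 and 6.2.5 by progression to multiple myeloma, not by the 5.11 list. The primary endpoint is response graded under 6.2.2. A removal before response could in principle cost a response, but nothing in the documents allows this to be sized, so no effect on the 2/16 rule is claimed.

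The conclusion assumes that the 5.11 limbs are complete as read. It does not rely on the gap in 6.2.2(g).

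**What to change.** 1. Add to the anemia limb in 5.11 the same sole-attribution clause that closes the calcium and creatinine limbs.
2. Change the creatinine clearance value in 5.11 from > 40 to < 40 ml/min, in line with 5.1.2.1. Record this as a separate correction.
3. State in 5.11 that progression is as defined in 6.2.2(g), and check against the full text of 6.2.2(g) that the organ limbs match.

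The cost is protocol wording. Blood counts and chemistry are already scheduled on Day 1 of each cycle (5.6.1.2). There are two downsides. Each hemoglobin fall past the trigger will need a recorded judgment of cause. Anemia of mixed cause would no longer count as progression by itself, although the M-protein, marrow and bone limbs would still apply.

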5.7.1.2 Dose Modification

Adverse events (both non-serious and serious) associated with pembrolizumab exposure may represent an immunologic etiology. These adverse events may occur shortly after the first dose or several months after the last dose of treatment.

Pembrolizumab must be withheld for drug-related serious adverse events grade 4 or higher or intolerable side effects.

Additionally, pembrolizumab must be withheld for drug-related toxicities and severe or life-threatening AEs as per Table 3 below. See Section 5.9 and Events of Clinical Interest Guidance Document for supportive care guidelines, including use of corticosteroids.

Table 3

Dose Modification Guidelines for Drug-Related Adverse Events

Toxicity	Hold Treatment For Grade	Timing for Restarting Treatment	Discontinue Subject
Diarrhea/Colitis	2-3	Toxicity resolves to Grade 0-1.	Toxicity does not resolve within 12 weeks of last dose or inability to reduce corticosteroid to 10 mg or less of prednisone or equivalent per day within 12 weeks.
	4	Permanently discontinue	Permanently discontinue
AST, ALT, or Increased Bilirubin	2	Toxicity resolves to Grade 0-1	Toxicity does not resolve within 12 weeks of last dose.
	3-4	Permanently discontinue (see exception below) ¹	Permanently discontinue
Type 1 diabetes mellitus (if new onset) or Hyperglycemia	T1DM or 3-4	Hold pembrolizumab for new onset Type 1 diabetes mellitus or Grade 3-4 hyperglycemia associated with evidence of beta cell failure.	Resume pembrolizumab when patients are clinically and metabolically stable.
Hypophysitis	2-3	Toxicity resolves to Grade 0-1	Toxicity does not resolve within 12 weeks of last dose or inability to reduce corticosteroid to 10 mg or less of prednisone or equivalent

Toxicity	Hold Treatment For Grade	Timing for Restarting Treatment	Discontinue Subject
			per day within 12 weeks.
	4	Permanently discontinue	Permanently discontinue
Hyperthyroidism	3	Toxicity resolves to Grade 0-1	Toxicity does not resolve within 12 weeks of last dose or inability to reduce corticosteroid to 10 mg or less of prednisone or equivalent per day within 12 weeks.
	4	Permanently discontinue	Permanently discontinue
Hypothyroidism	2-4	Therapy with pembrolizumab can be continued while treatment for the thyroid disorder is instituted	Therapy with pembrolizumab can be continued while treatment for the thyroid disorder is instituted.
Infusion Reaction	3-4	Permanently discontinue	Permanently discontinue

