The End of Treatment and Follow-up visit procedures are listed in Section 7.0 (Study Calendar). After the end of treatment, each subject will be followed for 90 days for adverse event monitoring (serious adverse events will be collected for 90 days after the end of treatment as described in Section 7.0 (study calendar, adverse events/toxicity, footnotes ^{b,j}). Subjects who discontinue for reasons other than progressive disease will have post-treatment follow-up for disease status until disease progression, initiating a non-study cancer treatment, withdrawing consent or becoming lost to follow-up. After documented disease progression each subject will be followed by telephone for overall survival until death, withdrawal of consent, or the end of the study, whichever occurs first.

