6.0 DATA COLLECTION AND EVALUATION

6.1 Data Collection

Data will be prospectively collected and entered into a clinical trials database. The protocol specific data will be entered into Redcap, the electronic case report form. All data will be kept secure. Personal identifiers will not be used when collecting and storing data. An enrollment log will be maintained in the regulatory binder/file which is the only location of personal identifiers with unique subject identification number. The Investigator or physician designee is responsible for providing source documentation and assigning attribution for all AEs.

When patients enter the long-term follow-up period, the following data will be collected:

- Adverse events related to Pembrolizumab
- Survival status which will be collected by phone or clinic visit
- Additional cancer therapy received

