- g. Baseline bone marrow aspiration and biopsy will be sent to Department of Pathology, flow cytometry, FISH/cytogenetics, multiple myeloma tissue bank, gene expression profiling, whole exome sequencing, VDJ sequencing and storage.
- h. Bone marrow aspirate and biopsy can be performed +/- 21 days of intended cycle day. Bone marrow aspirate and biopsy will be sent to Department of Pathology, flow cytometry, FISH/cytogenetics, gene expression profiling, VDJ sequencing and storage.
- i. At minimum, follow-up will be every 6-12 months until progression of disease, institution of alternative therapy, or death. Patients may be followed at more frequent time intervals if clinically indicated, ie following post-therapy toxicity. Patients who have progressive disease while on study will be followed with restaging scans and laboratory tests as clinically indicated. Patients who are taken off treatment will continue to be followed for survival by phone or clinic visit.
- j. Variations of +/- 14 days of scheduled visits are permitted.
- k. Variations of +/- 3 days of scheduled visits are permitted.
- l. Peripheral blood sample only.
- m. If clinically indicated
- n. All concomitant medications received within 28 days before the first dose of trial treatment and 30 days after the last dose of trial treatment should be recorded in the medical record.

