8.2 Assessing and Recording Adverse Events

An adverse event is defined as any untoward medical occurrence in a patient or clinical investigation subject administered a pharmaceutical product and which does not necessarily have to have a causal relationship with this treatment. An adverse event can therefore be any unfavorable and unintended sign (including an abnormal laboratory finding, for example), symptom, or disease temporally associated with the use of a medicinal product or protocol-specified procedure, whether or not considered related to the medicinal product or protocol-specified procedure. Any worsening (i.e., any clinically significant adverse change in frequency and/or intensity) of a preexisting condition that is temporally associated with the use of the Merck's product, is also an adverse event.

Changes resulting from normal growth and development that do not vary significantly in frequency or severity from expected levels are not to be considered adverse events. Examples of this may include, but are not limited to, teething, typical crying in infants and children and onset of menses or menopause occurring at a physiologically appropriate time.

Merck product includes any pharmaceutical product, biological product, device, diagnostic agent or protocol-specified procedure, whether investigational (including placebo or active comparator medication) or marketed, manufactured by, licensed by, provided by or distributed by Merck for human use.

Adverse events may occur during the course of the use of Merck product in clinical trials or within the follow-up period specified by the protocol, or prescribed in clinical practice, from overdose (whether accidental or intentional), from abuse and from withdrawal.

Adverse events may also occur in screened subjects during any pre-allocation baseline period as a result of a protocol-specified intervention, including washout or discontinuation of usual therapy, diet, placebo treatment or a procedure.

Progression of the cancer under study is not considered an adverse event unless it is considered to be drug related by the investigator.

All adverse events will be recorded in Redcap from the time the consent form is signed through 90 days following cessation of treatment and at each examination on the Adverse Event case report forms/worksheets. The reporting timeframe for adverse events meeting any serious criteria is described in section 8.2.3.1.

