- Unless otherwise noted, the electronic SAE application (eSAE) will be utilized for safety reporting to the IND Office and MDACC IRB.
- Serious adverse events will be captured from the time of the first protocol-specific intervention, until 90 days after the last study treatment/intervention, unless the participant withdraws consent. Serious adverse events must be followed until clinical recovery is complete and laboratory tests have returned to baseline, progression of the event has stabilized, or there has been acceptable resolution of the event.
- Additionally, any serious adverse events that occur after the 30 day time period that are related to the study treatment must be reported to the IND Office. This may include the development of a secondary malignancy.

Reporting to FDA:

- Serious adverse events will be forwarded to FDA by the IND Sponsor (Safety Project Manager IND Office) according to 21 CFR 312.32.

It is the responsibility of the PI and the research team to ensure that serious adverse events are reported according to the Code of Federal Regulations, Good Clinical Practices, the protocol guidelines, the sponsor's guidelines, and Institutional Review Board policy.

Investigator Communication with Supporting Companies:

A serious adverse event is any adverse event occurring at any dose or during any use of Merck's product that:

- Results in death;
- Is life threatening;
- Results in persistent or significant disability/incapacity;
- Results in or prolongs an existing inpatient hospitalization;
- Is a congenital anomaly/birth defect;
- Is a new cancer (that is not a condition of the study);
- Is associated with an overdose;
- Is another important medical event

Refer to Table 5 for additional details regarding each of the above criteria.

Any serious adverse event, or follow up to a serious adverse event, including death due to any cause other than progression of the cancer under study that occurs to any subject from the time the consent is signed through 90 days following cessation of treatment, or the initiation of new anti-cancer therapy, whichever is earlier, whether or not related to Merck product, must be reported within 24 hours to the Sponsor and within 2 working days to Merck Global Safety.

Non-serious Events of Clinical Interest will be forwarded to Merck Global Safety and will be handled in the same manner as SAEs.

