8.2.3.2 Events of Clinical Interest

Selected non-serious and serious adverse events are also known as Events of Clinical Interest (ECI) and must be recorded as such on the Adverse Event case report forms/worksheets and reported within 24 hours to the Sponsor and within 2 working days to Merck Global Safety. (Attn: Worldwide Product Safety; [contact]) Events of clinical interest for this trial include:

1. an overdose of Merck product, as defined in Section 8.2.1 - Definition of an Overdose for This Protocol and Reporting of Overdose to the Sponsor, that is not associated with clinical symptoms or abnormal laboratory results.
2. an elevated AST or ALT lab value that is greater than or equal to 3X the upper limit of normal and an elevated total bilirubin lab value that is greater than or equal to 2X the upper limit of normal and, at the same time, an alkaline phosphatase lab value that is less than 2X the upper limit of normal, as determined by way of protocol-specified laboratory testing or unscheduled laboratory testing.*

*Note: These criteria are based upon available regulatory guidance documents. The purpose of the criteria is to specify a threshold of abnormal hepatic tests that may require

an additional evaluation for an underlying etiology. The trial site guidance for assessment and follow up of these criteria can be found in the Investigator Trial File Binder (or equivalent).

1. Additional adverse events:

A separate guidance document has been provided entitled “Event of Clinical Interest Guidance Document” (previously entitled, “Event of Clinical Interest and Immune-Related Adverse Event Guidance Document”). This document can be found in the appendices and provides guidance regarding identification, evaluation and management of ECIs and irAEs.

ECIs (both non-serious and serious adverse events) identified in this guidance document from the date of first dose through 90 days following cessation of treatment, or 30 days after the initiation of a new anticancer therapy, whichever is earlier, need to be reported within 24 hours to the Sponsor and within 2 working days to Merck Global Safety. (Attn: Worldwide Product Safety; [contact]), regardless of attribution to study treatment, consistent with standard SAE reporting guidelines.

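### The 90-day safety window after treatment has no scheduled general safety contact or safety laboratory test behind it from about day 21 onwards

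*Combined protocol and SAP*

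**What the plan says.** Four places in the protocol set the same horizon.

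- Section 5.11: "After the end of treatment, each subject will be followed for 90 days for adverse event monitoring".
- Section 8.2: "All adverse events will be recorded in Redcap from the time the consent form is signed through 90 days following cessation of treatment".
- Section 8.2.3.1 captures serious adverse events "until 90 days after the last study treatment/intervention, unless the participant withdraws consent".
- Section 8.2.3.2 makes the events of clinical interest in the guidance document reportable "from the date of first dose through 90 days following cessation of treatment", or to 30 days after new anticancer therapy if that comes first.

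For the procedures, Section 5.11 sends the reader to the Section 7.0 calendar, and for the 90-day collection to its footnotes b and j. Footnote b lists the viral tests. Footnote j reads: "Variations of +/- 14 days of scheduled visits are permitted".

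After the dosing visits the calendar has three columns: end of cycle 8 or 24, disease progression, and follow-up. All three include examination, routine laboratory tests and adverse events. There is no column for end of treatment as such, day 30 or day 90. Footnote i sets the follow-up timing: "At minimum, follow-up will be every 6-12 months until progression of disease, institution of alternative therapy, or death". It allows more frequent visits where clinically indicated. Section 8.1.2.1.1 moves a patient into follow-up on completing 8 or 24 cycles or on confirmed progression, with clinic visits as the calendar provides.

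On when toxicity may appear, Section 5.7.1.2 says of events linked to the drug: "These adverse events may occur shortly after the first dose or several months after the last dose of treatment". Section 6.1 lists the data taken in long-term follow-up, among them "Adverse events related to Pembrolizumab".

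**The concern.** Safety and tolerability is a secondary objective (Section 3.2), and the patients are asymptomatic. The protocol itself expects some toxicity to appear months after dosing ends, and it sets a 90-day window to catch it. A site that follows the calendar exactly could still make no general safety contact and draw no safety blood sample for most of that window.

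This matters most for events that show only in the laboratory. The hepatic event of clinical interest in Section 8.2.3.2 is defined entirely by AST or ALT, bilirubin and alkaline phosphatase values. Thyroid and pancreatic enzyme changes can also be silent. The same section ties the routine check for events of clinical interest to the time before each dose, so that check ends with dosing.

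Section 9.0 reports toxicity as frequency tables in all treated patients. With 16 patients, one patient whose event is missed moves a rate by 1/16, or 6.25 percentage points.

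**Working it through.** The plan gives no figure for this gap, so there is nothing to reproduce. The check is calendar arithmetic.

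**Inputs**
- Safety window: 90 days (Sections 5.11, 8.2, 8.2.3.1 and 8.2.3.2).
- Cycle length: 21 days, dosing on day 1 (Sections 2.1 and 5.7). The end-of-cycle visit is therefore taken as day 21 after the last dose. This is inferred; the protocol gives no day.
- Visit windows: 3 days either way for cycle visits (footnote k), 14 days either way for follow-up (footnote j).
- Follow-up: at minimum every 6 to 12 months (footnote i). No starting point is given, so I count from the last dose.
- Pregnancy test at day 28 after the last dose for women of childbearing potential, or days 14 and 28 with irregular menstruation (footnote e).

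**Days without a scheduled general assessment** = 90 − day of last scheduled visit
- Visit at day 21: 90 − 21 = 69 days; 69/90 = 77%.
- Visit at day 18 or 24: 72 or 66 days; 80% or 73%.
- Visit as late as day 35 (21 + 14): 55 days; 61%.
- Counting the day 28 pregnancy test as a contact: 90 − 28 = 62 days; 69%.

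**First follow-up visit under the minimum schedule**
- 6 months = 182.6 days. With the 14-day allowance the earliest is 182.6 − 14 = day 169, which is 79 days after the window has closed.
- 12 months = 365.25 days. The earliest is day 351, which is 261 days after it has closed.
- Counted from the end-of-cycle visit instead, the 6-month visit falls at about day 204, 114 days after closure.

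Under each of these assumptions, the minimum schedule puts the first required follow-up visit outside the window.

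**Can the under-count be sized?** No. The documents give neither a rate of delayed events nor a detection rate. Purely as an illustration, assume a 5% to 20% risk per patient of a delayed event in the gap, with 25% to 100% of these missed:
- Expected missed events: from 16 × 0.05 × 0.25 = 0.2 to 16 × 0.20 × 1 = 3.2.
- Chance of missing at least one: from 1 − (1 − 0.0125)^16 = 18% to 1 − (1 − 0.20)^16 = 97%.

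The range is too wide to support any statement about size.

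**Scope of collection.** Section 8.2 covers all adverse events to day 90. The parenthesis in Section 5.11 mentions only serious ones. Section 6.1 lists only drug-related events in long-term follow-up, a period whose start is not defined. Section 8.2.3.1 refers to serious events after a 30-day period directly beneath its own 90-day rule.

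**The case against.** Several points on the other side are sound.

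- A reader might infer that nothing at all is scheduled. That is not so. Footnote e sets pregnancy tests after the last dose, and concomitant medications are recorded for 30 days (Section 5.8.1, footnote n). Neither is a general safety assessment, no visit is attached to the medication record, and neither runs to day 90.
- A reader might infer that patients are not seen for at least 6 months. Footnote i sets a minimum frequency and allows earlier visits; Section 8.1.1.2 likewise allows more frequent assessment. The restart rule in Section 2.1, which turns on progression within 6 months of stopping, also presupposes some contact. But these are permissions or implications without a date, and a silent laboratory event gives no indication for a visit.
- Patients who progress are not limited to telephone calls. The progression column includes laboratory tests and adverse events, footnote i allows further tests as indicated, and Section 8.1.2.1.1 provides for clinic visits. Still, none of these fixes an assessment within the 90 days after the last dose.
- A reader might infer that toxicity rates are biased downward. The documents do not establish that. Symptomatic events can be volunteered or recalled later, events present at discontinuation are followed (Section 8.1.2.1), and related serious events are reportable whenever they come to light (Section 8.2.3.1).
- The scope passages can be read together: all events to day 90, related events afterwards. That reading is reasonable, but the protocol does not state it.

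The guidance document on events of clinical interest (Section 12.2) is not reproduced in the text I reviewed. If it fixes contacts after treatment, the remaining point would be to bring them into the calendar.

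**Conclusion.** The point holds as a mismatch between promise and schedule. The protocol commits to 90 days of safety ascertainment, but the calendar fixes no general safety contact or safety laboratory test from about day 21 to day 90, and the cited footnotes do not supply one. The uncovered stretch is about 69 days (range 55 to 72), or 62 days where the day 28 pregnancy test counts as a contact.

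These figures rest on an end-of-cycle visit near day 21, in patients who complete 8 or 24 cycles. A patient who stops early has the final-visit activities at discontinuation, so the uncovered stretch may differ. The 6-to-12-month comparison further assumes that follow-up is counted from the last dose or from the end-of-cycle visit.

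The supported consequence is a risk that delayed events, chiefly asymptomatic laboratory ones, are missed or recorded with the wrong onset date or grade. That events are in fact under-counted, and by how much, cannot be shown from the documents. The primary endpoint, the two-stage rule and the sample size are unaffected. The change should be made, because the stated calendar cannot by itself deliver the ascertainment that a secondary objective relies on.

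**What to change.** 1. Add to the Section 7.0 calendar, for every treated patient including those who progressed, a scheduled safety contact at or near day 90 after the last dose. It could be by telephone. Attach the existing routine laboratory panel of footnote a at a time the sponsor chooses. The exact timing, and any additional earlier call, are the sponsor's decision.
2. In Section 5.11, replace the pointer to footnotes b and j with a pointer to this new row.
3. Reconcile Sections 5.11, 6.1, 7.0, 8.2 and 8.2.3.1. State once that all adverse events are collected through day 90 and related events after that, define when long-term follow-up begins, and resolve the 30-day reference.
4. State the day from which the 6-to-12-month follow-up visits are counted.

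The cost is a calendar amendment plus, for each of 16 patients, at least one contact and one routine blood draw. The downside is slightly more site work and possibly a somewhat higher reported toxicity rate, because more events would be found.
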